Exclusion criteria: Weight change of > 3.0 kg in the month prior to screening, weight loss of > 10 kg in the 6 months prior to screening, calorie restriction diet (< 1500 kcal/day) for a period of 4 months or more in the 12 months prior to screening, use of any other investigational drug(s) within 8 weeks prior to screening, abnormal baseline laboratory parameters (serum creatinine > 1.6 mg/dl; ALT, AST, total bilirubin > 2.0 times the upper limit of normal; triglycerides > 500 mg/dl, total cholesterol > 350 mg/dl, TSH outside of normal range), consumption of more than 1 alcoholic beverage per day, pregnancy or intention to become pregnant.

Consent: Veterans will be consented during their screening visit. They must sign the VA GLAHS Institutional Review Board-approved written informed consent prior to the initiation of any study specific procedures or randomization.

Enrollment and randomization: Date of birth, sex, race, medical history, current medications, smoking and alcohol history will be obtained by the study coordinator during the screening visit. Eligible subjects will be assigned an enrollment number after signing the informed consent form then will be randomized to one of two diet groups.

Dietary intervention: Participants will be randomized to a HPD (30% protein, 40% carbohydrate, 30% fat) or a NPD (15% protein, 55% carbohydrate, 30% fat) with matched fatty acid profiles and fiber content. The diet will be implemented in two phases: an initial macronutrient standardized diet without calorie restriction for 2 weeks then the same macronutrient standardized diet with 1500 calorie restriction for 14 weeks. Subjects will receive dietary counseling during their baseline visit on their assigned macronutrient standardized diet. After 2 weeks of a macronutrient standardized diet, both groups will then receive further dietary counseling on how to restrict their intake to 1500 calories. Pea-based protein supplements will be provided to the HPD group to achieve the target of 30% calories from protein in the HPD group.

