Nutritional assessments: Participants will complete a three-day food record (3DFR) and the Food Frequency Questionnaire (FFQ) at every study visit to assess adherence to the prescribed macronutrient composition and calorie limit of the two dietary groups. The 3DFR consists of detailed documentation of food eaten on three days. FFQ is a self-administered, semi-quantitative tool that queries the average frequency of consumption over the prior one month of a list of food items. It will be modified to cover only 2 weeks on study visits at weeks 2 and 4. This study will use the Diet History Questionnaire supported by the National Cancer Institute and previously validated against other FFQs. The extensive nutrient composition database that supports the questionnaire allows estimations of the intake of macronutrients (e.g. fats), micronutrients (e.g. carotenoids), and specific food groups such as fruits, vegetables and grains.

B. Measurement of clinical response to the dietary interventions.

Primary and secondary endpoints: The primary clinical endpoint for response to dietary intervention will be weight loss. Secondary measures of clinical response will include change in fat mass, liver steatosis, lipids, and HgbA1c.

Clinical data collection: The following parameters will be obtained on each of 7 study visits: baseline, week 2, week 4, week 6, week 8, week 12, and week 16.

- 1) Physical examination: The study coordinator will measure height, weight, and waist/hip circumference.
- 2) Bioelectrical impedance analysis (BIA): Electrodes attached to a BIA device will be placed on the wrists and ankles. A brief electrical current will be passed to measure resistance and reactance, which can be used to calculate lean body mass and fat mass. One BIA device will be dedicated to this study.
- 3) Liver transient elastography (FibroScan): Hepatic steatosis and fibrosis will be evaluated by transient elastography, a non-invasive test that can be performed in 5 minutes using equipment that will be available down the hall from the clinical research unit where study visits will occur. Steatosis will be assessed by the CAP score and fibrosis by elastography with stiffness measured in kilopascals.

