- 4) Laboratory studies: Blood samples will be collected by venipuncture after 8-14 hours of fasting. Complete blood count, chemistry panel, lipids (total cholesterol, LDL, HDL, triglycerides), and hemoglobin A1c (HgbA1c) will be measured by the clinical laboratory at the West Los Angeles VA Medical Center.

Statistical analysis: Patient characteristics (physical measurements, lean body mass, laboratories, demographic traits) at baseline will be compared using a 2-sided t-test (for numerical variables) or chi-square test (for categorical variables) to evaluate the randomization. 3DFR and FFQ performed at each time point will be used to assess the predicted protein content of the patient's diet compared to baseline to evaluate the success of the dietary intervention. The significance of differences between the two groups in the primary and secondary outcome measures will be assessed using a 2-sided t-test.

C. Kinetic analysis of shifts in microbial composition in obese subjects (BMI 27-40) on a high protein diet compared to an isocaloric normal protein diet.

Fecal sampling: Participants will be provided with kits for home sampling. The subjects will urinate first then defecate into the Fisherbrand Commode Specimen Collection System. Subjects will use a spoon to transfer freshly defecated feces to a Para-Pak stool collection cup prefilled with 95% ethanol to fix the samples, allowing storage at room temperature for up to 2 weeks. Ethanol-fixed and fresh frozen samples give comparable metagenomics results to samples stored in preservatives such as RNALater while minimizing subjects' risk of exposure to toxic chemicals. The remaining feces will be frozen. This involves removing the cup from the

toilet hat, tightly closing the lid, and transferring the cup to a Ziploc bag for storage in the subject's freezer. Frozen samples will be delivered to the VA clinic during scheduled study visits using a Styrofoam box containing U-tek freezer packs designed to maintain a temperature of -20°C as was performed for a recent study. Reminder calls will be made 4 days before each study visit. Subjects who forget to bring in samples will be asked to either bring them in at the next visit or send them via overnight FedEx delivery. Samples will be stored at -80°C.

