Microbiome analysis: DNA will be extracted from fecal samples collected in ethanol at baseline, day 3, day 7, week 2, day 17 (3 days after calorie restriction), day 21 (7 days after calorie restriction), week 4, week 6, week 8, week 12, and week 16 using the MO BIO Powersoil kit. Sequencing of the 253 base pair V4 region of 16S ribosomal DNA will be performed using the Illumina HiSeq 2500 to a depth of 250,000 reads per sample. Microbial diversity (alpha diversity) will be compared between the two dietary groups at each time point using the Chao1 index, Shannon index, and Faith's phylogenetic diversity. Significance will be determined using a non-parametric test (Mann-Whitney U). Microbial composition (beta diversity) will be compared across all samples using weighted UniFrac (a phylogenetic distance metric) and visualized by principal coordinates analysis (PCoA). Significance of differences in composition at each time point will be determined using Adonis, a permutation-based method. Baseline data will be analyzed to confirm that randomization had successfully eliminated pre-existing microbial differences between the two dietary groups.

Abundance of individual bacteria will then be fitted to multivariate models using DESeq2. This algorithm performs normalization using size factors estimated by the median-of-ratios method, employs an empirical Bayesian approach to shrink dispersion, and fits the data to negative binomial models. Diet group, time point, interaction between diet and time point, baseline BMI, age, sex, and smoking status will be covariates in the model. Diet composition parameters derived from the nutritional instruments (3DFR, FFQ) may also be included. This model will be compared to a reduced model that does not include the diet:time point interaction. A likelihood ratio test will be used to identify microbes with differential abundance by diet at time points after baseline. Estimates of significance will be adjusted for multiple hypothesis testing to calculate q-values, which represents the false discovery rate. Q-values less than 0.05 will be considered significant. Microbes that are differentially abundant on a HPD will be grouped by hierarchical clustering to highlight distinct kinetic patterns of microbial change.

D. Risk/benefit analysis

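### Weight loss and the secondary change measures are compared by an unadjusted t-test; a baseline-adjusted week-16 contrast from one mixed model is a cheap improvement using data already collected

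*Combined protocol and SAP*

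**What the plan says.** Section B, primary and secondary endpoints, states: "The primary clinical endpoint for response to dietary intervention will be weight loss". It continues: "Secondary measures of clinical response will include change in fat mass, liver steatosis, lipids, and HgbA1c". Under clinical data collection, "The following parameters will be obtained on each of 7 study visits", that is, at baseline and at six later visits ending at week 16.

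The statistical analysis paragraph of section B then gives the comparison: "The significance of differences between the two groups in the primary and secondary outcome measures will be assessed using a 2-sided t-test". It names no covariate, analysis visit, kg or percent scale, or rule for missing weights. The other stated use of baseline clinical values in that section is that they "at baseline will be compared using a 2-sided t-test (for numerical variables) or chi-square test (for categorical variables) to evaluate the randomization".

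Two facts in section A (dietary intervention) bear on this. The diet begins with "an initial macronutrient standardized diet without calorie restriction for 2 weeks", so the week-2 visit precedes calorie restriction. Also, "Pea-based protein supplements will be provided to the HPD group", and no supplement is mentioned for the other arm.

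Section C (microbiome analysis) plans a longitudinal, covariate-adjusted model for bacterial abundance: "Diet group, time point, interaction between diet and time point, baseline BMI, age, sex, and smoking status will be covariates in the model".

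**The concern.** The natural reading of weight loss and of the secondary measures is change from baseline. Baseline then enters by subtraction with a fixed coefficient of one. A covariate lets the data set that coefficient, which is usually more precise and costs one degree of freedom. The five visits between baseline and week 16 have no stated role in the clinical comparison, yet they carry information about anyone who misses week 16.

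At stake is precision for the clinical endpoints, mainly the secondary ones. If completers alone were compared, robustness to dropout would also be at stake. The plan already accepts modelling of this kind for bacteria.

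**Working it through.** **The plan's own figure.** Section A gives an estimated 216 participants, 1:1, so 108 per arm. It states no effect size, SD, power, clinical alpha or dropout rate, so 216 cannot be reproduced. Assuming two-sided alpha 0.05 and no dropout, 108 per arm detects (1.960 + 0.842) × √(2/108) = 0.381 SD at 80% power.

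**Baseline adjustment, complete data.** Let baseline and week-16 values have equal variance σ² and correlation rho.
- Variance of change: 2σ²(1 − rho).
- Residual variance given baseline: σ²(1 − rho²).
- Ratio, adjusted to change score: (1 − rho²) / [2(1 − rho)] = (1 + rho)/2, a reduction of (1 − rho)/2.

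For weight, assume a change SD of 6 kg. Then rho = 1 − 36/(2 × SD²), which is 0.900, 0.930 and 0.950 at weight SDs of 13.4, 16 and 19 kg. The last column starts from an effect for which the change-score t-test has 80% power.

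| Assumed rho | Variance ratio | Reduction | Equivalent extra participants, 216/ratio − 216 | Power instead of 80% |
|---|---|---|---|---|
| 0.95 | 0.975 | 2.5% | 5.5 | 81.0% |
| 0.90 | 0.950 | 5% | 11.4 | 82.0% |
| 0.80 | 0.900 | 10% | 24 | 84.0% |
| 0.50 | 0.750 | 25% | 72 | 89.9% |

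The first two rows are plausible for weight; the last two are possible for less stable secondary measures. If change is unrelated to baseline, the best coefficient is already one and nothing is gained (simulated ratio 1.006). With complete data, the mixed model specified under the fix gives the same week-16 contrast as ANCOVA.

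**Missing week-16 weights (illustration only).** Every input here is assumed: 108 per arm, mean losses of 5 and 7 kg, change following a random walk that reaches SD 6 kg at week 16 plus 1 kg noise, and dropout after weeks 2 to 12. A completer t-test is set against the mixed model.
- *Precision, completely random dropout of 10–30%.* The variance ratio runs from 0.974 to 0.833 across weight SDs and slopes on baseline, so the model's variance is 3–17% lower. When dropout depends on response the gain was smaller: ratios of 0.94–0.97 at SD 16 kg, and 0.975–0.985 with no slope on baseline.
- *Bias, dropout depending on the last observed weight, SD 16 kg.* Sizes are in kg. Log-hazard slopes of 0.5 and 1 per standardised unit of poorer response are called moderate and strong.

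| Scenario | Completer t-test, moderate | Completer t-test, strong |
|---|---|---|
| Same process in both arms, 10/20/30% dropout | 0.02/0.04/0.08 | 0.07/0.10/0.19 |
| Same dependence, 15% v 25% dropout | 0.23 | 0.34 |
| Same dependence, 10% v 30% dropout | 0.39 | 0.71 |
| Dependence in one arm only, 10/20/30% dropout | 0.18/0.38/0.60 | 0.35/0.71/1.05 |

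Mixed-model bias was within 0.03 kg throughout. Sizeable t-test bias therefore needs the arms to differ, but a difference in rate is enough; the dependence need not be confined to one arm.
- *Dropout depending on the next, unseen weight, strong, one arm, 10/20/30%.* The t-test bias was 0.42/0.85/1.31 kg and the model bias 0.16/0.32/0.52 kg. The model helps but does not remove it.

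**The case against.** The strongest reply is that the plan is sound for its purpose. A t-test on change is unbiased under randomisation with complete data. Week 16 ends both treatment and follow-up, so it is the obvious visit even though it is not named. For weight itself the gain from adjustment is 2.5–5% at best, and the stated hypothesis concerns the microbiome. All of this stands, and it limits the point to an improvement in the clinical analysis.

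Two criticisms of the calculations also stand. The secondary-measure correlations are assumed, and fat mass may track its baseline as closely as weight does. The dropout scenarios suit the mixed model by construction and let weight loss start at week 0. Starting it at week 2, in line with the diet's first phase, cut the bias for strong dependence in one arm at 20% dropout from 0.72 to 0.53 kg in a separate run.

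A reader might infer three stronger things that the documents do not support.
- *That the t-test is invalid.* It is not, for change at one visit with complete data.
- *That the unnamed visit inflates the false-positive rate.* This would require testing several visits or choosing one after seeing the data, and the documents plan neither. The missing visit and scale are mostly missing detail.
- *That dropout will bias the result by some tenths of a kilogram or more.* No dropout rate is given, and nothing links the supplements to dropout. With the same process in both arms, the bias is negligible against standard errors of 0.85–0.99 kg.

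**Conclusion.** The point holds as a cheap improvement. The planned comparison leaves out each outcome's baseline as a covariate and gives the intermediate visits no role, although both are already collected. With equal SDs, the gain over a change-score t-test is 2.5–5% of variance at rho 0.95–0.90 and 10–25% at rho 0.8–0.5; these correlations are assumptions.

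The second benefit is conditional. It arises only if week-16 values are missing and completers alone would be compared, and the bias advantage needs dropout that depends on earlier weights and differs between arms in rate or dependence. The kilogram figures illustrate that mechanism and do not estimate it for this trial.

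**What to change.** In the statistical analysis paragraph of section B:
- Define the single primary clinical test as the week-16 diet contrast in weight change (kg) from one repeated-measures mixed model. Its terms are diet, visit, diet × visit, baseline weight and baseline weight × visit, with unstructured covariance.
- Include every randomised participant with at least one post-baseline weight, in the assigned arm. ANCOVA at week 16 alone could not include people without a week-16 weight unless it were imputed.
- Treat other visits and percent change as supportive.
- Use the same model for each secondary measure with its own baseline, log-transforming skewed measures such as triglycerides.
- State how missing values are handled, and add one sensitivity analysis for data not missing at random, for example imputed week-16 weights shifted by arm over a stated range.

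The cost is SAP wording and slightly more analysis work; no new data, visits or participants are needed. The downsides are a small gain for weight itself and reliance on a missing-at-random assumption, which the sensitivity analysis is there to probe.

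### Forty post-baseline diversity tests have no stated multiplicity correction, and the alpha-diversity tests leave the collected baseline sample unused

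*Combined protocol and SAP*

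**What the plan says.** Section C, Microbiome analysis, lists stool samples at baseline and at day 3, day 7, week 2, day 17, day 21 and weeks 4, 6, 8, 12 and 16. Section D.1.a gives the same total of eleven collections.

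For alpha diversity, the groups "will be compared between the two dietary groups at each time point using the Chao1 index, Shannon index" and Faith's phylogenetic diversity. The test is stated as "Significance will be determined using a non-parametric test (Mann-Whitney U"). For beta diversity, on weighted UniFrac distances: "Significance of differences in composition at each time point will be determined using Adonis, a permutation-based method". The only use given for baseline in this part is a check: "Baseline data will be analyzed to confirm that randomization had successfully eliminated pre-existing microbial differences".

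The next paragraph fits DESeq2 models to individual bacteria, with covariates and a diet-by-time interaction. It then says "Estimates of significance will be adjusted for multiple hypothesis testing to calculate q-values", with q below 0.05 counted as significant. That sentence follows the likelihood ratio test for microbes. Nothing comparable is said about the diversity tests, and no primary index or primary time is named for them.

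On weight, Section B says "The primary clinical endpoint for response to dietary intervention will be weight loss", with measurements at seven visits. Its Statistical analysis paragraph says "The significance of differences between the two groups in the primary and secondary outcome measures will be assessed using a 2-sided t-test". It names no visit, analysis set or rule for missing data.

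**The concern.** Section C applies error control to one set of microbiome tests and is silent on its neighbours. Ten of the uncorrected tests, the Adonis tests, bear directly on the hypothesis in Section A that the diet shifts microbial composition. Reading significance time by time, a few nominal results can be expected by chance and could be reported as part of the kinetic pattern that Section C sets out to describe.

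The second issue is efficiency. Each participant provides a baseline stool sample, but Mann-Whitney on post-baseline values takes no covariate and the plan names no change score. The precision available from that sample is not used for alpha diversity.

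A lesser issue is that a t-test needs one value per person. If it is run at week 16 on available data, participants who leave drop out of the primary clinical comparison along with the weights already recorded for them.

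**Working it through.** **Number of tests.** Eleven stool times less baseline leaves 10. Three alpha indices × 10 = 30 Mann-Whitney tests, plus 1 × 10 = 10 Adonis tests, makes 40.

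**False positives.** The plan states no level for these tests, so 5% two-sided is assumed. The expected number under the null is 40 × 0.05 = 2.0 whatever the correlation: 1.5 from the alpha indices and 0.5 from Adonis. The chance of at least one depends on how strongly the results at different times are correlated. The documents do not give this, so a range is shown for one family of ten tests (simulated):

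| Between-time correlation | One alpha index, uncorrected | Adonis, uncorrected |
|---|---|---|
| 0.9 | 13% | 13–14% |
| 0.7 | 21% | 22% |
| 0.5 | 29% | 29–30% |

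After Benjamini-Hochberg over the ten times, the figures are 2.7–4.3% for an alpha index and 2.7–4.8% for Adonis.

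**Value of the baseline sample.** Section A gives 216 participants at 1:1, so n = 108 per arm. Assume a true shift of 0.3 SD, complete data and the same correlation r between all sampling times. For a normal outcome, power at one time is Φ(0.3 × √(108/2) / √(1 − r²) − 1.96).
- Without baseline (r = 0 in the formula): Φ(2.20 − 1.96) = 60%. Mann-Whitney loses a little; simulation gives 57%.
- With baseline, r = 0.5: Φ(2.20/0.866 − 1.96) = Φ(0.59) = 72%.
- With baseline, r = 0.7: Φ(2.20/0.714 − 1.96) = Φ(1.13) = 87%.

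Rank-based analysis of covariance (ANCOVA) gives somewhat less. Simulated power:

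| r | Rank ANCOVA, one time, uncorrected | FDR over ten times: shift at all ten | FDR: shift at weeks 6–16 only | FDR: shift at one time only |
|---|---|---|---|---|
| 0.3 | 61% | 50% | 37% | 29% |
| 0.5 | 68% | 60% | 48% | 35% |
| 0.6 | 75% | 68% | 55% | 44% |
| 0.7 | 83% | 78% | 66% | 53% |

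The comparator is 57% for the current uncorrected Mann-Whitney test. The FDR columns are per-time power within one index; correcting across the three indices as well can lower them.

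**Why baseline adjustment alone is not enough.** Removing baseline lowers the correlation between the ten tests from r to r/(1 + r): 0.33, 0.375 and 0.41 at r = 0.5, 0.6 and 0.7. The chance of at least one uncorrected false positive is then 31–35%, against 23–29% for Mann-Whitney at the same r.

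**Weight (secondary).** The documents give no effect size, SD or dropout rate. Assume a true difference of 1.5 kg, SD 4.5 kg, the week 16 visit and 20% dropout after week 2.
- Complete data: SE = 4.5 × √(2/108) = 0.612 kg; power Φ(1.5/0.612 − 1.96) = 69%.
- Dropout unrelated to outcome: the t-test on those remaining has simulated SE 0.674–0.696 kg, giving power of 60–58%. A likelihood analysis using earlier visits has SE 0.641 kg, giving 65%. There is no bias in this case.
- Dropout more likely after less weight loss, with the same rule in both arms: the t-test is biased toward zero by 0.03–0.25 kg.

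**The case against.** **The main hypothesis is largely protected.** The specific prediction in Section A, increased *Akkermansia*, is tested by DESeq2 with q-values. This stands, and nothing here extends to that analysis. Thirty of the forty tests concern alpha diversity, which is not part of the stated hypothesis. They can fairly be called descriptive, but the plan still says that their significance will be determined. The ten Adonis tests are closer to the hypothesis.

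**Mann-Whitney on randomised groups is valid.** This also stands. Omitting baseline costs precision and does not bias the comparison. The gain depends on an assumed correlation. At r = 0.3, corrected power is 50% or lower in every pattern examined, below the present 57%. A reader might infer that baseline adjustment always pays for the correction; it does so only for a sustained shift with r of about 0.5 or more.

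**The weight point rests on silence.** It does. A reader might infer that the plan prescribes a biased completers-only analysis. The documents do not say so: they name no visit, no exclusion of those who leave and no dropout rate, and the t-test is valid with complete data. Bias of 0.31–0.95 kg can be produced at 20% dropout, in either direction, but only if leaving depends on weight loss in one arm alone. That is an extreme case, and nothing in the documents suggests it.

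**Conclusion.** The diversity point holds. Forty post-baseline tests have no stated correction beside a microbe-level analysis that has one, and the alpha-diversity tests do not use baseline. At an assumed 5% level this means about 2 expected false positives under the null, and about a 13–29% chance of at least one in each ten-time family at between-time correlations of 0.9–0.5.

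A reader might multiply out 1 − 0.95^40 = 87% for at least one false positive. That requires independent tests. These come from the same participants sampled repeatedly, with three indices computed on the same samples. With moderate to strong correlation, the figure over all forty ranges from 67% (0.5 across times, 0.5 across measures) to 26% (0.9 and 0.8).

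The weight point is a secondary improvement and not a demonstrated error. At an assumed 20% dropout it is worth about 5–7 points of power, and avoids most of a 0.03–0.25 kg bias if leaving depends on earlier weight loss in the same way in both arms. The change should be made. Confidence is medium because the correlations, SDs and dropout are assumed.

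**What to change.** 1. FDR-adjust the ten post-baseline Adonis p-values, and the alpha-diversity p-values across times and indices, using the q < 0.05 rule that Section C already applies to microbes.
2. Replace the Mann-Whitney tests with baseline-adjusted comparisons, such as rank ANCOVA or a baseline-adjusted longitudinal model. Keep the time-specific contrasts so that the kinetic aim is preserved. A joint or average test over time is optional.
3. As a secondary change, name week 16 as the visit for weight loss. Estimate the diet contrast there from a baseline-adjusted repeated-measures model over weeks 2–16 in all randomised participants. State the missing-at-random assumption and add one sensitivity analysis that departs from it.

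The cost is SAP wording and modest analysis work, with no new data. Fewer diversity results will be nominally significant. An alpha-diversity shift confined to one time is harder to detect (29–53% against 57%, and possibly lower with correction across indices). The Adonis correction brings no offsetting gain in power. The weight result would rest on missing at random.

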Study Protocol and Statistical Analysis Plan

Modulation of the Intestinal Microbiome by a High Protein Diet

NCT04812964

Document date: April 5, 2018

STUDY PROTOCOL: Modulation of the Intestinal Microbiome by a High Protein Diet

A. Design of randomized, controlled study comparing high and normal protein isocaloric calorie restriction diets for obesity.

Rationale and hypothesis: Based on my preclinical rodent model data, I hypothesize that a high protein diet will shift the composition of the microbiome of obese subjects, including increased *Akkermansia*, and that this will be associated with alterations of the metagenome (bacterial genes) and metabolome.

Study design: This hypothesis will be investigated in a randomized controlled study of the intestinal microbiome of an estimated 216 obese Veterans assigned 1:1 to isocaloric high protein (HPD) or normal protein (NPD) diets. The study will be advertised by posting flyers in the West Los Angeles VA Medical Center MOVE obesity clinic. MOVE physicians will provide interested patients with information about the study. Participants will undergo an initial screening visit in the clinical research unit after their MOVE appointment or on a later date. Once enrolled, participants will return to the clinical research unit for a baseline visit and follow-up visits on weeks 2, 4, 6, 8, 12, and 16 for dietary counseling, physical measurements, phlebotomy, and dietary questionnaires. The recruitment rate is estimated as 7 per month based on the recently completed study led by [name]. Patient recruitment and sample collection will be performed during the first 3 years of the study.

Inclusion criteria: Men and women between 20 and 75 years of age, BMI 27 to 40 kg/m², non-smoker or stable smoking habits for at least 6 months prior to screening and agreement not to change such habits during the study; subjects on non-obesity prescription medication may be included.

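### Composition and alpha diversity are compared between diets at each stool time point without the participant's own baseline sample, which costs power and leaves chance baseline imbalance in the result

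*Combined protocol and SAP*

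**What the plan says.** All references are to the combined protocol and SAP.

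- **Composition** (section C, Microbiome analysis): "Significance of differences in composition at each time point will be determined using Adonis, a permutation-based method". The metric is weighted UniFrac. No covariate, change from baseline or distance to the participant's own earlier sample is stated.
- **Alpha diversity** (same section): "Microbial diversity (alpha diversity) will be compared between the two dietary groups at each time point using the Chao1 index, Shannon index, and Faith's phylogenetic". Each of these three indices is tested by Mann-Whitney U. Again no baseline term is stated.
- **Time points** (same section): "baseline, day 3, day 7, week 2, day 17 (3 days after calorie restriction), day 21 (7 days after calorie restriction), week 4, week 6", then weeks 8, 12 and 16. That makes 11 stool samples, 10 of them after baseline.
- **Role given to baseline microbiome data** (same section): "Baseline data will be analyzed to confirm that randomization had successfully eliminated pre-existing microbial differences between the two dietary groups".
- **Baseline patient characteristics** (section B, Statistical analysis): these "will be compared using a 2-sided t-test (for numerical variables) or chi-square test (for categorical variables) to evaluate the randomization".
- **Single taxa** (section C, DESeq2): "Diet group, time point, interaction between diet and time point, baseline BMI, age, sex, and smoking status will be covariates in the model". The full model is compared with one that drops the interaction.
- **Size** (section A, Study design): "an estimated 216 obese Veterans assigned 1:1 to isocaloric high protein (HPD) or normal protein (NPD) diets", so 108 per arm.

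**The concern.** The hypothesis in section A and the title of section C are about a shift in the microbiome. A between-arm test at one follow-up time compares cross-sections. Stable differences between people stay in the error term, although a baseline stool that could remove part of them is already collected.

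The plan instead uses baseline to judge the randomization. Randomization does not eliminate differences; it makes them due to chance. If allocation was carried out properly, a baseline p-value tests a hypothesis already known to be true, and a large p-value does not show that the arms are alike. An imbalance that passes the check is carried, in proportion to the baseline-to-follow-up correlation, into the later cross-sectional comparisons.

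Two things are at stake: power to detect a real community-level effect of diet, and the reading of these comparisons in a trial that happens to draw an unlucky baseline.

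**Working it through.** **Inputs.** From the document: 216 participants, 1:1, so n = 108 per arm; 11 stool time points. The document gives no power calculation, effect size, SD or baseline-to-follow-up correlation, so there is no figure of its own to reproduce. Assumed: two-sided alpha 0.05 (the only stated threshold is q < 0.05 for the taxon tests), a correlation r between 0.3 and 0.8, and an illustrative difference of 0.3 SD. A single normally distributed measure stands in for one axis of composition or one diversity index.

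**1. What the baseline check can show.** The standard error of a baseline difference, in SD units, is sqrt(2/108) = 0.136. Imbalances up to 1.96 × 0.136 = 0.27 SD are non-significant. Power to flag a true imbalance is 0.31 at 0.2 SD and 0.45 at 0.25 SD; 80% power needs 0.38 SD. In the other direction, the plan implies four microbiome tests at baseline (three alpha indices and Adonis). If they were independent, the chance of at least one p < 0.05 under sound randomization would be 1 − 0.95^4 = 0.185.

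**2. Power lost by leaving baseline out.** Adjustment multiplies the residual variance by 1 − r². The test statistic has mean 0.3 / [0.136 × sqrt(1 − r²)], and power is the probability that it exceeds 1.96 in absolute value.

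| r | 1 − r² | Mean of z | Power |
|---|---|---|---|
| unadjusted | 1 | 2.20 | 0.60 |
| 0.3 | 0.91 | 2.31 | 0.64 |
| 0.5 | 0.75 | 2.55 | 0.72 |
| 0.7 | 0.51 | 3.09 | 0.87 |

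A small simulation of an Adonis-type permutation test (Euclidean distance, 10 dimensions, shift of 0.15 SD per dimension, 400 runs, 199 permutations) points the same way. Power was 0.67 unadjusted against 0.79 adjusted at r = 0.5, and 0.62 against 0.94 at r = 0.7. With no shift, both analyses rejected in about 4% to 6.5% of runs.

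**3. Type I error of the unadjusted follow-up test.** Given a baseline statistic z0 and no diet effect, the follow-up statistic is normal with mean r × z0 and variance 1 − r².

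- Over all randomizations: 5%, whatever r is.
- Over randomizations that pass the baseline check (|z0| < 1.96): 4.3%, 4.0%, 3.5% and 3.0% at r = 0.5, 0.6, 0.7 and 0.8.
- Given an imbalance of 0.25 SD (z0 = 0.25/0.136 = 1.84, p = 0.066, a pass): 11.5% at r = 0.5 and 17.3% at r = 0.7.
- Given z0 = 1.9, just under the cut-off: 12% at r = 0.5 to 23% at r = 0.8. Only 0.7% of randomizations have |z0| between 1.9 and 1.96.

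**4. The taxon model.** In DESeq2, baseline is one level of time and the tested term is diet by time. A constant difference between arms falls in the diet main effect, not in the tested interaction.

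**The case against.** The strongest reply is that nothing here is invalid. The comparison is randomized, the unadjusted test has its nominal level, and among trials that pass the baseline check its average error is below 5%. That stands. A reader might infer from the 12% to 23% figures that the Adonis tests are anti-conservative. They are not: those figures describe a near-worst draw.

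A reader might also infer that every microbiome result can mistake a baseline difference for a diet effect. The document does not support that either. The named organism, *Akkermansia*, is a single-taxon question, and the DESeq2 interaction already separates a constant baseline difference between arms. That model has no participant term, but this is a separate matter.

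A third tempting reading is that the plan will declare randomization failed on a significant result, or makes later analyses depend on the check. No such rule is written. The microbiome sentence names no test and no threshold; that significance tests are meant follows from the methods given for each time point, of which baseline is one, and from section B, where the tests are explicit. Nor does the plan forbid a baseline term in Adonis; it omits one. Looking at baseline for faults in allocation is also not pointless, though p-values are a weak tool for it.

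Last, chances of a false alarm across the whole clinical baseline table depend on how many tests are run and on their independence. The document fixes neither, and the variables are plainly correlated, so no figure for that table is relied on here.

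**Conclusion.** The point holds as one of precision and interpretation, of moderate weight. Adonis and the Mann-Whitney tests leave out a baseline sample that is already collected, and the one separate use stated for baseline microbiome data is a confirmation that a significance test cannot give. In the univariate illustration the power forgone is 0.04, 0.12 and 0.27 at r = 0.3, 0.5 and 0.7 (0.64, 0.72 and 0.87 less 0.60). The second cost is conditional bias in the minority of trials with a sizeable chance imbalance.

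These sizes rest on an assumed alpha, effect size and correlation, and on a single-axis analogue of a multivariate test. If the true correlation is low, the gain is small. Removing the baseline p-values alone would change little; the gain comes from the adjustment.

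**What to change.** In section C (Microbiome analysis):

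- At each of the 10 post-baseline time points, run Adonis with a pre-specified number of the participant's baseline weighted UniFrac principal-coordinate scores entered before diet.
- Compare each alpha-diversity index between arms adjusted for its baseline value.
- State that both adjustments are made whatever the baseline comparison shows.
- Replace the sentence on confirming the randomization with a description of baseline by arm using standardized differences. Do the same for the tests in section B that are meant to judge the randomization.

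No new samples or visits are needed; the cost is wording and a few lines of code. There are two downsides. The number of axes is an analyst's choice and must be fixed before the data are seen. Participants without a baseline stool either leave the adjusted test or need a missing-baseline indicator, and the plan should say which. Distance from the participant's own baseline sample is an alternative to the axis scores; if it is preferred, it should be named in advance.
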